## Précis

As life expectancy increases and acute cardiac mortality decreases, the incidence of chronic heart failure (HF) continues to rise, and despite this, conceptual advances in the treatment of chronic heart failure have not increased substantially over last few decades. One intracellular component of heart failure progression is mitochondrial bioenergetic dysfunction. Although the mechanism underpinning this is not completely understood, recent metabolomics data demonstrated an incomplete flux of metabolites through oxidative phosphorylation (OX PHOS) in HF. In parallel, data has shown that hyperacetylation of mitochondrial bioenergetic enzymes, with the concomitant blunting of enzymatic activity is evident in HF. Putting these together, an emerging hypothesis implicates excessive acetylation of mitochondrial proteins with the subsequent blunting of bioenergetic enzyme function, as a mechanism underpinning incomplete flux through OX PHOS resulting in HF progression.

In parallel with cardiac bioenergetic deficiency chronic HF subjects display disrupted skeletal muscle OX PHOS, which is thought to contribute towards overall fatigue and reduced exercise tolerance. Interestingly exercise training in HF subjects improves skeletal muscle mitochondrial OX PHOS capacity and subject activity levels. Exercise training additionally increases activity of the mitochondrial regulatory deacetylase sirtuin enzymes SIRT1 and SIRT3, in parallel with improved skeletal muscle OX PHOS capacity. At the same time HF-associated disruption in skeletal muscle metabolic function activates skeletal muscle cytokine production. These inflammatory programs, in turn, are proposed to contribute towards impaired functional capacity in HF. Interestingly, and mirroring improved OX PHOS following exercise programs in HF studies, exercise training similarly reduces skeletal muscle inflammatory effects.

Biochemical and bioenergetic consequences of impaired mitochondrial OX PHOS leads to decreased NAD+ levels, which exacerbate mitochondrial dysfunction by inactivating the NAD+ dependent sirtuin enzymes. Experimental studies using NAD+ precursors to increase NAD+ production have been shown to normalize NADH/NAD+ ratios and activate Sirtuin enzymes, resulting in enhanced OX PHOS with beneficial effects in numerous systems including skeletal muscle and in the blunting of inflammation.

In this pilot study we will **directly** assess the effect of the NAD+ precursor, nicotinamide riboside (NR) on skeletal muscle mitochondrial OX PHOS in HF subjects using: skeletal muscle NMR spectroscopy assessment of the rate of high energy phosphate recovery in response to submaximal exercise; assessment of the effect of NR on functional capacity using cardiopulmonary exercise testing (CPET) to determine VO2max and anaerobic threshold; evaluation of the NR effect on serum metabolomics at rest and in response to CPET; and by measuring circulating cytokine levels pre- and post- NR administration. These studies would enable a more comprehensive assessment of the role for NR supplementation on skeletal muscle mitochondrial function in subjects with systolic HF.

## 1. Background

As a result of life expectancy increases and a reduction in acute cardiac mortality, the incidence of chronic heart failure is rising with approximately 900,000 new diagnoses per annum. Despite this increasing burden of disease, conceptual advances in the treatment of chronic heart failure have not increased substantially over the last few decades.

One component of heart failure progression, which is also emerging as a biomarker of poor outcome, is the development of mitochondrial dysfunction with concomitant bioenergetic deficits. Prior therapeutic approaches to abrogate or delay bioenergetic deficiency focused on directing and augmenting specific substrate utilization in the heart. However, studies to date have not shown convincing benefit and/or gave rise to unacceptable side effects. A possible reason for the lack of efficacy of this approach may have been uncovered by metabolomics analyses, which have found that mitochondrial bioenergetic defects associated with chronic heart failure are associated with incomplete metabolism of substrates through metabolic pathways with evidence of a bottleneck of carbon flux through mitochondrial oxidative phosphorylation pathways. In parallel, data support that hyperacetylation of mitochondrial bioenergetic enzymes, with the concomitant blunting of enzymatic activity, may be a mechanism underpinning this incomplete metabolic flux. At the same time biochemical data show that acetylation of mitochondrial proteins plays an important post-translational regulatory role in the blunting of mitochondrial energetic function and in exacerbating mitochondrial production of reactive oxygen species. Together, these data suggest that excess acetylation of mitochondrial proteins blunt bioenergetic enzyme function and may play a role in the progressive disruption in mitochondrial bioenergetic functional integrity.

In parallel with cardiac bioenergetic deficiency subjects with chronic heart failure also show disruption of skeletal muscle oxidative phosphorylation. These skeletal muscle changes are thought to contribute towards overall fatigue and reduced exercise tolerance in heart failure. Interestingly, using exercise training as an intervention to improve heart failure patient activity levels also improves muscle mitochondrial oxidative phosphorylation capacity. Exercise training additionally increases the activity of the mitochondrial regulatory deacetylase sirtuin enzymes SIRT1 and SIRT3, in parallel with improved skeletal muscle oxidative phosphorylation capacity. At the same time, serum obtained from exercising individuals compared to sedentary individuals demonstrated augmented mitochondrial function in skin fibroblasts when their serum was used to condition the fibroblast growth media. Additionally heart failure associated disruption in skeletal muscle metabolic function plays a role in activating skeletal muscle cytokine production. These inflammatory programs are proposed to contribute towards the detrimental effects on heart failure patient functional capacity. Interestingly, and mirroring improved oxidative phosphorylation following exercise programs in heart failure studies, exercise training has also been found to reduce skeletal muscle inflammatory effects.

Biochemical and bioenergetic consequences of impaired mitochondrial oxidative phosphorylation leads to decreased NAD+ levels, which in turn appears to exacerbate

mitochondrial dysfunction by inactivating the NAD+ dependent sirtuin enzymes. Experimental studies using NAD+ precursors (including nicotinamide mononucleotide (NMN) and nicotinamide riboside (NR)) to increase NAD+ production through the NAD+ salvage pathway have been shown to normalize the NADH/NAD+ ratio and activate Sirtuin enzymes, which in turn function to improve mitochondrial function with beneficial effects in numerous systems including skeletal muscle and in suppressing inflammation.

## Preliminary Results

Recently, our collaborators at the University of Washington (UW) demonstrated in a murine model, that impaired mitochondrial oxidative phosphorylation led to a decreased myocardial NAD+/NADH ratio and increased mitochondrial protein acetylation. These changes rendered the heart susceptible to chronic stresses, which accelerated the development of heart failure. They observed a similar decrease in NAD+/NADH ratio and an increase in protein acetylation in animal models of heart failure due to chronic pressure overload with no prior mitochondrial dysfunction. Supplying the NAD+ precursor, nicotinamide mononucleotide (NMN), to these mice normalized the NAD+/NADH ratio, prevented increased mitochondrial protein acetylation and improved cardiac function. Though NMN is not orally bioavailable, we and others have shown that oral supplementation with nicotinamide riboside (NR), the precursor from which NMN is produced, also decreases (normalizes) tissue NAD+/NADH ratio and improves mitochondrial function in mouse models. Together, these animal model results suggest a conceptually innovative mechanism linking mitochondrial dysfunction to the development and

[figure not shown]
progression of heart failure. Additionally, NR may be a useful nutritional supplement to increase NAD+ levels, thereby normalizing the NAD+/NADH ratio caused by mitochondrial dysfunction during chronic stresses, and potentially improve functional capacity and ventricular function in systolic heart failure.

Our UW collaborators completed a pharmacokinetics study (NCT02689882). NR was supplied as 250 mg capsules by the manufacturer (Niagen®, ChromaDex, Irvine, CA). NR was manufactured in a GMP-compliant facility according to ISO/IEC 18025:2005 standards. Two Certificates of Analysis provided by the manufacturer and performed on separate lots reported ~99% purity of the NR preparation. In addition, an independent analysis was performed at the University of Washington on NR (Niagen®) purchased online (Amazon.com, Inc., Seattle, WA) by the investigators; H-NMR spectroscopy of this NR demonstrated 98-99% purity (Figure 1).

**Figure 1. Typical H NMR spectrum of an aqueous extract (in deuterated water) of a NR capsule obtained on a Bruker AVANCE III 800 MHz nuclear magnetic resonance (NMR) spectrometer.** NMR signals that arise from NR are labeled with the corresponding location of the hydrogen atom(s) as shown in the molecular structure of NR (inset). TSP [3-(trimethylsilyl)propionic acid-2,2,3,3-d4 sodium salt] was used as an internal standard to quantify the amount and purity of NR in the capsules. The purity of NR was calculated based on integration of all the peaks and was in the range of 98-99%.

Eight subjects participated in this PK study and NR in incremental doses up to 1 gram bid was administered over 9 days. The mean basal (Day 1) circulating level of NAD+ was  $18 \pm 4$   $\mu\text{g/mL}$ , consistent with values reported previously in healthy subjects. Nicotinamide adenosine dinucleotide (NADH) was not detected in blood. Nicotinamide mononucleotide (NMN), a known immediate precursor of NAD+, was detected in Baseline (Day 1) blood samples of all subjects but was at or just above the assay lower limit of quantitation. Notable elevations in blood NAD+ concentrations were seen on Day 9 compared to Baseline on Day 1 in every subject (Figure 2). Blood NAD+ was, on average, about 2-fold higher than Baseline (range 1.34- to 2.66-fold), with a mean increase of 17.7  $\mu\text{g/mL}$  ( $p = 0.001$ ). As a group, the rise in blood NAD+ following NR treatment did not correlate with the basal blood level on Day 1 ( $R^2 = 0.27$ ,  $p = 0.2$ ).

**Figure 2. Concentration-time curves for NAD+.** Each subject is depicted in a different color with time points connected by a line. The y-axis depicts NAD+ concentrations in ng/ml, and the x-axis depicts values on Day 1 (baseline) and then time post-dose in hours on Day 9. The baseline time point was collected pre-dose on Day 1 of the trial.

**This study revealed no significant side effects and the primary pre-specified safety data**

**showed no changes in levels of potassium, glucose, uric acid, creatine kinase or alanine aminotransferase levels (data not shown). The subjects also displayed no changes in hemodynamics, although the hematocrit dropped from  $40 \pm 3$  to  $39 \pm 3$  (percent) and the platelets dropped from  $220 \pm 40$  to  $200 \pm 30$  ( $\times 10^3/\mu\text{L}$ ), both  $\pm\text{SD}$  with a  $p$  value  $< 0.05$ . The modest reduction in hematocrit, hemoglobin and platelet count were suspected to result from the repeated daily laboratory blood draws over the nine-day study.**

At the same time we recently found that NR improves mitochondrial oxidative phosphorylation capacity in parallel with suppressing in-vitro inflammation in human peripheral blood cells. Hence, given the role of skeletal muscle in heart failure inflammation, we will also measure serum cytokine levels in response to NR in this protocol.

Additional studies have been completed or are ongoing using NR to study effects on mitochondrial biology related conditions including aging (at the University of Colorado in Boulder – PI - Drs [name] - actively recruiting) and in heart failure (University of Washington in Seattle – [name] [name] - actively recruiting). Based on their prior pharmacokinetics study described above the University of Seattle team are using 1000mg BID in their Heart Failure protocol. To date, they have recruited 15 subjects and the dose of 1000 mg BID has been well tolerated. We therefore propose to use the same, 1000mg BID dosing.

## **Hypothesis**

NR supplementation in stable NYHA FC II-III heart failure subjects will improve skeletal muscle mitochondrial function.

## **Proposed Scientific/Clinical Innovations and Advances of the Study**

- Evaluate whether pharmacologic activation of Sirtuin enzymes by NR will enhance mitochondrial oxidative phosphorylation in skeletal muscle of heart failure subjects.
- Use metabolomics to evaluate whether NR can ameliorate the bottleneck in metabolic flux through the oxidative phosphorylation pathway in HF subjects.
- Expand our understanding of the role of disrupted oxidative phosphorylation on inflammation in heart failure.

## **2. Objectives**

A pilot study will be undertaken where up to 25 participants with clinically stable, systolic heart failure (LVEF  $\leq 45\%$ ) will be enrolled with a goal of having 15 subjects complete the treatment. NR will be increased at two weekly intervals by 250 mg/dose (500 mg/day) to a final dose of 1000mg PO BID (2000 mg/day). Clinic visits with bi-weekly labs during dose escalation will assess HF symptoms and monitor proBNP, CBC, HbA1C, ALT, CK, insulin/glucose, uric acid, electrolytes, BUN/Cr levels. Serum NAD+ levels will be measured at baseline, 12 and 16 weeks and baseline (within 3 months of enrollment) and 12 week echocardiograms will be performed to measure left ventricular systolic and diastolic function.

## **Scientific Aims: Determine the effects of NR on skeletal muscle oxidative phosphorylation capacity in heart failure:**

- A) Baseline, 12-week ( $\pm 5$ -days) (on NR) and 16-week ( $\pm 5$ -days) (4-week washout) skeletal muscle fixed-load sub-maximal exercise NMR spectroscopy to assay skeletal muscle phosphocreatine recovery time as a measure of mitochondrial oxidative phosphorylation.
- B) Baseline and 12-week ( $\pm 5$ -days) cardiopulmonary testing to assay VO2max and anaerobic thresholds.
- C) Baseline and 12-week ( $\pm 5$ -days) serum quantitative metabolomic profiling, pre- and post-CPET to evaluate whether NR increases the rate of oxidative phosphorylation.
- D) Baseline and 12-week ( $\pm 5$ -days) quantitative serum cytokine immunoassay profiling to assess whether NR blunts HF linked inflammation.
- E) Skin biopsy at baseline and research blood at baseline and 12 weeks ( $\pm 5$ -days) to explore the effects of NR on oxidative phosphorylation and inflammation in respective subject primary skin fibroblasts.

### 3. Study Design and Procedures

The study design is an open label pilot study with subjects serving as their own controls. The outline of the clinical protocol is shown in a tabular schematic below.

Visit #	1	2	3	4	5	6	7A/B	8	9
Weeks	-1 to -3	0	0+ 1-2 days	2	4	6	12	12 + 1-2 days	16
Procedures									
History	X	X		X	X	X	X		X
Physical exam	X			X	X	X	X		X
Initiate NR/dispense meds			X						
Dose adjustment				X 	X 	X 			
Stop NR								X	
Urine pregnancy test	X 	X 	X 				X 	X 	X 
Clinical blood tests	(X)	X 	X 	X	X	X	X 	X 	X
NMR spectroscopy		X 	X 				X 	X 	X
CPET		X 	X 				X 	X 	
Echo	X*						X		
Research blood		X 	X 					X 	
Skin biopsy		X 	X 						
AE assessment				X	X	X	X	X	X
Concomitant meds/tx	X			X	X	X	X	X	X
Study drug adherence				X	X	X	X		
Key:									
(X) Performed only if baseline laboratory studies not performed during routine testing within 6 months									
X Procedure performed									
 Increase NR dose by 250mg BID									
 Pregnancy test will only be performed in women with childbearing potential. It can be completed at Visit 1, 2 and/or 3 and Visit 7 or 8									
 Skin biopsy will be completed at either Visit 2 or 3.									
 NMR spectroscopy, clinical and research blood, and CPET testing can be performed at either Visit 2 or 3 for baseline timepoint and Visit 7 or 8 for end of treatment timepoint.									
* Procedure is optional (Echo is optional on Visit 1 if PI feels there is an adequate and timely historical Echo)									
Visits 1, 4, 5, 6, and 7 may take place at either WRNMMC or NIH Clinical Center.									
Visits 2, 3, 7B, 8, and 9 will take place at the NIH Clinical Center									

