### **Visit 3 (Week 0 + 1-2 days, NIH CC)**

#### **The following procedures will be performed at Visit 3:**

- Dispense NR: Level 1 ( 250mg PO BID to initiate supplementation in evening after visit 3).
- Dispense Level 2-4 bottles of NR: Level 2 (500mg PO BID – to initiate after visit 4), Level 3 (750mg PO BID – to initiate after visit 5) and Level 4 (1000mg PO BID – to initiate after visit 6 and maintain through visit 7).

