## **Visit 6 (Week 6, WRNMMC or NIH CC)**

**The following procedures will be performed at the follow-up visits (Day 42±5):**

- Medical history, physical examination, current medical treatments
- Blood draws will analyze: CBC+Diff, BNP, HbA1C, uric acid, ALT, CK, Chemistry panel (electrolytes, glucose, blood urea nitrogen and creatinine) and insulin levels.
- Record of adverse events, if any
- Study drug adherence with pill count and collect Level 3 NR 750mg PO BID bottle
- Record of concomitant medications or interventions, if any
- Communicate the initiation of Level 4 NR 1000mg PO BID in evening after visit 6

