## **Visit 7 (Week 12, WRNMMC and/or NIH CC)**

**The following procedures will be performed at the follow-up visit (Day 84 ± 5):**

- 7A WRNMMC (Day 84 +/-5) Medical history, physical examination, current medical treatments
- Blood draws will analyze: CBC+Diff, proBNP, HbA1C, uric acid, ALT, CK, Chemistry panel (electrolytes, glucose, blood urea nitrogen and creatinine) and insulin levels.
- Record of adverse events, if any
- Study drug adherence with pill count
- Record of concomitant medications or interventions, if any
- Continue Level 4 NR - 1000mg PO BID
- Echocardiography

7B NIH (Day 84+/-5)

- Pregnancy test on women with childbearing potential (may be performed at Visit 7 or 8)

- Skeletal muscle exercise NMR spectroscopy or CPET
- Research blood if CPET performed at this visit

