### **Visit 8 (Visit 7B + 1-3 days, NIH CC)**

- CPET or Skeletal muscle exercise NMR spectroscopy (whichever was not done at Visit 7B)
- Research blood if CPET performed at this visit
- Pregnancy test on women with childbearing potential (may be performed at Visit 7 or 8)
- Record of adverse events, if any
- Study drug adherence with pill count
- Discontinue NR
- Record of concomitant medications or interventions, if any

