### **Adverse Event Management**

The principal investigators at WRNMMC or NIH, or designees, will be responsible for assessing adverse events. Information on adverse events will be solicited from subjects through questions from study personnel and information volunteered by the subject. Adverse events will be captured from the start of the first pill taken (day 0) until the completion of the washout phase of the study. The AEs will be attributed (unrelated, unlikely, possibly, probably or definitely) to study supplement and/or disease. This study will utilize the CTCAE version 5.0 for toxicity and adverse event reporting. A copy of the CTCAE version 5.0 can be downloaded from the [https://ctep.cancer.gov/protocolDevelopment/electronic\\_applications/ctc.htm](https://ctep.cancer.gov/protocolDevelopment/electronic_applications/ctc.htm). AEs will be recorded, verified, and followed until satisfactory resolution.

In the event of any treatment-related SAEs, enrollment will be suspended until discussed with the IRB and Clinical Director.

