- **Skin biopsy:** This procedure is performed using local anesthetic. After washing the skin with alcohol and numbing the skin, a 4 mm or smaller circle of skin is removed steriley and the wound is dressed. The entire procedure takes approximately 5 minutes. Discomfort at the biopsy site is usually mild and transient. This can be treated with minor analgesics. Normally, the risks include a reaction to the local anesthetic and the slight possibilities of local bleeding or infection. Scarring always occurs at the biopsy site.
- **MR Spectroscopy:**

MRI uses non-ionizing radiation and is safe when used on subjects that are appropriately screened for the procedure. Subjects with any exclusionary criteria (Pregnancy, Aneurysm clip, implanted devices such as neural stimulators, cardiac pacemaker, defibrillator, cochlear implant, foreign body, such as, metal shavings, or insulin pumps, will be excluded from the study.

Potential risks of MRI relate to effects of the main, static magnetic field, the applied radiofrequency (RF) power, and the rapidly switching magnetic field gradients. The risks associated with each of these are described below. We will stay within all the FDA guidelines for the applied RF power, the rate of switching magnetic fields and the noise levels that these switching gradients produce (see Guidance for Magnetic Resonance Diagnostic Devices – Criteria for Significant Risk Investigations, issued July 14, 2003. <http://www.fda.gov/cdrh/ode/guidance/793.pdf>).

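### No pregnancy test is scheduled on NR until dosing is ending or over, and the week-12 test is permitted after the muscle scan from which pregnant women are excluded

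*Combined protocol and SAP*

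**What the plan says.** **Testing.** In the Section 3 schedule table the urine pregnancy test is marked at Visits 1, 2, 3, 7, 8 and 9 and is blank at Visits 4, 5 and 6. Note 2 limits it to women with childbearing potential and adds: "It can be completed at Visit 1, 2 and/or 3 and Visit 7 or 8". The procedure lists for Visits 4, 5 and 6 contain no pregnancy test. βHCG appears only among the laboratory tests in Section 4.

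**Dosing.** NR is dispensed at Visit 3, "to initiate supplementation in evening after visit 3". The dose rises after Visits 4, 5 and 6; the Visit 6 list reads "Communicate the initiation of Level 4 NR 1000mg PO BID in evening after visit 6". NR is stopped at Visit 8.

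**Week 12.** The Visit 7B list has "Pregnancy test on women with childbearing potential (may be performed at Visit 7 or 8", followed by "Skeletal muscle exercise NMR spectroscopy or CPET". Visit 8, headed as 1 to 3 days after Visit 7B, has "CPET or Skeletal muscle exercise NMR spectroscopy (whichever was not done at Visit 7B" and repeats the same option for the pregnancy test.

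**Safeguards.** Section 4 excludes pregnant women and those unwilling to use contraception or abstain. Section 11 requires contraception while enrolled and says that safety of NR in pregnancy has not been determined. Section 9 withdraws women found to be pregnant, and Section 10 covers reporting. For the scan, Section 11 (Risks and Discomforts) names pregnancy first among the reasons for exclusion: "Subjects with any exclusionary criteria (Pregnancy, Aneurysm clip, implanted devices such as neural stimulators".

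**The concern.** The withdrawal rule protects a woman only once the pregnancy is known. The schedule places the first on-treatment test where a positive result can spare little or no NR. A pregnancy that begins early and goes unrecognised could pass through all four dose levels before a scheduled test. This avoidable exposure to a supplement of undetermined safety in pregnancy is the main point.

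The second point is order. If the week-12 scan is done at Visit 7B and the pregnancy test at Visit 8, the result arrives after the scan and cannot serve the exclusion that Section 11 sets for it.

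**Working it through.** The plan gives no figure on this point to reproduce. The check sets the visit calendar against the dosing.

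**Inputs.**
- Visit 1 is 1 to 3 weeks before week 0, that is Day −21 to −7 with Visit 2 as Day 0. Visit 3 is 1 to 2 days after Visit 2 (schedule table).
- Visit 6 is Day 42 ± 5 and Visit 7 is Day 84 ± 5 (visit headings).
- Visit 8 is 1 to 3 days after Visit 7B by its heading. The schedule table says 1 to 2 days; this shortens the maxima by one day.
- Day 0 has two readings. The table puts week 0 at Visit 2 (anchor A). Section 10, Adverse Event Management, puts it at the first dose: "Adverse events will be captured from the start of the first pill taken (day 0". That is the day of Visit 3, so Visit 2 is Day −1 or −2 (anchor B).

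**Gap between tests as the plan stands.**
- Nominal, Visit 2 or 3 to Visit 7. A: 84 − 2 = 82 to 84 − 0 = 84 days. B: 84 − 0 = 84 to 84 + 2 = 86 days.
- Longest, Visit 2 to Visit 8. A: 84 + 5 + 3 − 0 = 92 days. B: 92 + 2 = 94 days.
- Longest if a Visit 1 test alone suffices, as note 2 can be read. A: 92 + 21 = 113 days.
- Days on NR before the first on-treatment test (A, with NR starting on Day 1 or 2): from 79 − 2 = 77 to 92 − 1 = 91.

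**NR left to withhold after that first test.** At Visit 7B: 1 to 3 days × 2 g = 2 to 6 g. At Visit 8: none.

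**Gap with a Visit 6 test.**
- With a baseline test at Visit 2 or 3. A: the larger of 47 − 0 = 47 and 92 − 37 = 55, so 55 days. B: the larger of 47 + 2 = 49 and 55, so 55 days.
- If Visit 1 alone still suffices (A): 47 + 21 = 68 days. The 55-day figure therefore needs both the Visit 6 test and the change to note 2.

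**NR that follows Visit 6.** From the daily doses in Section 6, using D for the visit days with the first pill as Day 0:
- Before Visit 6: 14 × 0.5 + 14 × 1.0 + 14 × 1.5 = 7 + 14 + 21 = 42 g.
- After Visit 6: 42 × 2.0 = 84 g. The total is 126 g, and 84/126 = 67%.
- Within the visit windows Level 4 lasts 80 − 47 = 33 to 92 − 37 = 55 days, or 66 to 110 g. NR before Visit 6 is 1.5 × D6 − 0.5 × D5 − 0.5 × D4. This gives 55.5 − 15.5 − 8.5 = 31.5 g (Days 37, 31, 17) to 70.5 − 12.5 − 5.5 = 52.5 g (Days 47, 25, 11). The share after Visit 6 runs from 66/118.5 = 56% to 110/141.5 = 78%.

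These shares are ceilings on what a Visit 6 test could spare. They apply only to a pregnancy that the test can detect on that day and that nothing else has brought to light. For a later conception the Visit 6 test spares nothing.

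**Scan order at week 12.** The scan and the test may each fall at Visit 7B or Visit 8, and no text ties one to the other. If both are at the same visit, or the test is at 7B and the scan at 8, a result can be in hand beforehand. Only the scan at 7B with the test at 8 puts the test 1 to 3 days late (1 to 2 by the table).

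**The case against.** The plan sets no testing interval that the schedule breaks, and it controls pregnancy by other means. It excludes pregnant women, requires contraception or abstinence, and tests before dosing, at the end of dosing and after washout. History, examination and adverse-event review take place at Visits 4 to 6, and a pregnancy found by any route leads to withdrawal. All of this lowers the risk, and choosing Visit 6 over Visit 4 or 5 is a matter of judgement. Even then, up to 49 days could pass between a Visit 2 test and the start of Level 4. But these measures do not replace a test. Contraception is asked about by telephone and confirmed at screening, with no later check listed at Visits 4 to 6. The plan itself does not rely on contraception alone, since it tests again at Visit 9, four weeks after NR stops.

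On the scan, a reader might infer that pregnant women would be scanned unscreened at week 12. The documents do not support that. The late test is permitted, not required, and the Visit 7B list itself names the test ahead of the scan. Section 11 describes MRI as safe for people suitably screened and says that pregnant subjects will be excluded. The scan is non-ionizing and classed as non-significant risk. Practice in the MRI unit is not described and the consent pages are not in the reviewed text, so a local check before the scan cannot be ruled out. What stands is that nothing in the plan requires a negative result first.

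**Conclusion.** The concern holds as a minor participant-safety point. Scheduled testing cannot bring the withdrawal rule into play during escalation or most of Level 4. The longest gap is 92 to 94 days from a Visit 2 test, and up to 113 days (Visit 2 as Day 0) if a Visit 1 test alone is accepted. The order of test and scan is a secondary matter of clarification.

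Two stronger readings should be resisted. One is that women may start NR untested. Pregnancy is an exclusion, tests are listed at Visits 1 to 3, and every permitted baseline test precedes the first dose, so baseline is not a material exposure gap. Note 2 against the visit lists is a drafting inconsistency. The other is that a Visit 6 test would save 84 g of NR per pregnancy, or prevent a known amount of harm. The 84 g is a ceiling on the nominal schedule, under the conditions given above, and the documents give no relation between dose and risk.

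The number of women of childbearing potential is not stated; it is assumed to be small among at most 25 subjects. The endpoint, sample size and primary analysis are unaffected.

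**What to change.** 1. In note 2 and the Visit 7 and 8 lists, require a negative urine test before the week-12 scan, at whichever of Visit 7B or 8 the scan takes place. State the same rule for the baseline and Visit 9 scans; the Visit 9 list already names the test first. This only orders tests that are already scheduled, so it is free.
2. Align note 2 with the lists for Visit 2 and for Visit 2 or 3, so that a Visit 1 test alone does not suffice. This is an edit to the text.
3. Add one urine test for women of childbearing potential at Visit 6, before Level 4 starts. The cost is one dipstick per woman at an existing visit. Screening tests are already done at either site, so both can run it.

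A positive result before the week-12 scan would lose that measurement, but the plan already excludes such a woman from the scan and withdraws her.
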